7.3. Ethical, legal and security issues

Screened participants will be listed in a confidential “subject screening log” and attributed a unique study ID. The codes will be linked with the participant’s identity on a separate file (subject identification list) and filed in a secured place at PHL-IdC and will only be accessible to investigators. Personal data will be coded for data analysis. No names will be published at any time, and published reports will not allow for identification of single subjects. Confidentiality will be ensured throughout the entire research project. All databases will be password secured. None of the investigators declare to have any conflicts of interest.

7.4. Data storage and preservation

Each stool sample will be destroyed once a duplicate Kato-Katz thick smear has been prepared. Slides will be destroyed up to one day after the examination and quality control are complete. Data and related material will be preserved for a minimum of 15 years to enable understanding of what was done, how and why, which allow the work to be assessed retrospectively and repeated if necessary. The primary data storage and backup will be in the Swiss TPH shared server and secondary data storage will be: personal laptops of [name] and [name], Swiss TPH shared server, and SWICTHdrive. All files stored in these locations will be password protected. Archiving conditions will be made strictly confidential by password protection.

7.5. Study documents: translations – reference language

- ICF: Master-document English, all language version are translation thereof.

- Caregiver knowledge assessment questionnaire: Master-document English, all language version are translation thereof.

8. Statistical analysis

8.1. Definition of primary endpoint

The primary endpoint of this study is the ERR of mebendazole against hookworm assessed 14 to 21 days post-treatment using the duplicate Kato-Katz thick smear method.

8.2. Justification of number of trial subjects

Because the primary outcome – difference in egg reduction rates (ERR) – does not follow a known distribution we ran a series of conservative simulations using data from Speich *et al.* [22] to determine the required sample size. An initial round of simulations showed that differences in ERRs are associated with substantial higher power compared to CRs. We used Monte Carlo resampling techniques to simulate CR of 10 and 20%, respectively, which translates roughly into ERRs of 38% and 64%. We estimated that 160 patients per arm are required to detect a statistical significant difference with 80% power. To account for potential loss to follow up (which was low in our previous studies in this setting) of 10% and to include a safety margin of 14% we aim to recruit in total 200 participants per trial arm.

8.3. Description of statistical methods

The primary analysis will use the full analysis set (available case population) according to the intention to treat principle defined as all randomized subjects which provide any follow-up data. Only subjects which were negative at baseline and erroneously randomized will be excluded from the analysis. Palatability and ease of swallowing are critical attributes in children; therefore, a per-protocol analysis will be conducted additionally to disentangle drug efficacy from adherence effects.

Geometric mean egg counts will be calculated for the different treatment arms before and after treatment to assess the corresponding ERRs. The ERR will be calculated as:

$$ERR = 1 - \frac{\frac{1}{n} e^{\sum \log(EPG_{follow-up} + 1)} - 1}{\frac{1}{n} e^{\sum \log(EPG_{baseline} + 1)} - 1}$$

Bootstrap resampling with 5,000 replicates will be used to calculate 95% confidence intervals (CIs) for ERRs and the difference between the two ERRs. Superiority will be claimed if the 95% confidence interval of the difference in ERRs does not include unity (primary hypothesis).

Differences in CRs will be assessed using unadjusted logistic regressions. In a subsequent analysis an adjusted logistic regression (adjustment for age, sex, weight and strata) will be performed.

AEs will be evaluated descriptively as the difference of proportion reporting AEs before and after treatment.

9. Duties of the investigator

The investigators are responsible for an adequate data quality. Prior to the initiation of the study, a short investigator's meeting will be held with the investigators and their study coordinators and a member from Swiss TPH. This meeting will include a detailed discussion of the protocol, performance of study procedures (SOPs from previous studies available on site), CRF completion, and specimen collection and diagnostic methods.

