4.3.3. Assessment of efficacy after treatment

The efficacy of the treatment in participants will be determined 14-21 days post-treatment by collecting another two stool samples, which will be microscopically examined for STH using duplicate Kato-Katz thick smears, creating a total of four slides for this time point assessment. Participants will be considered hookworm cured if no eggs were found in the follow-up stool samples.

EPG will be assessed by adding up the egg counts from the quadruplicate Kato-Katz thick smears and multiplying this number by a factor of six. Geometric and arithmetic mean egg counts will be calculated for the two treatment arms before and after treatment to assess the corresponding ERRs. Individuals will not be included in the trial if the hookworm EPG < 100 (total of the four slides) and/or if there is only one Kato-Katz thick smear slide with a hookworm egg.

Once all follow-up samples have been analysed, all participants who were still found STH-positive will receive albendazole (400 mg single dose) and ivermectin (200 $\mu\text{g}/\text{kg}$), which is currently recommended against STH by the WHO's Essential Medicines List.

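### The ERR formula puts 1/n outside the exponential, so it is not a geometric mean and returns about 100% in both arms or overflows

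*Combined protocol and SAP*

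**What the plan says.** The statistical methods section (8.3) first names the measure in words: "Geometric mean egg counts will be calculated for the different treatment arms before and after treatment to assess the corresponding ERRs". It then states how the ERR will be calculated, as 1 minus a ratio of two terms. In the extracted typesetting code, the fraction 1/n stands before the exponential in both:

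- follow-up term (numerator): "1}{n} e^{\sum \log(EPG_{follow-up} + 1)} - 1"
- baseline term (denominator): "1}{n} e^{\sum \log(EPG_{baseline} + 1)} - 1"

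The same section takes bootstrap confidence intervals for each ERR and for the difference between arms, and decides superiority from the interval for the difference.

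The document contains no other ERR formula. Section 4.3.3 describes the measure in words and names two kinds of mean: "Geometric and arithmetic mean egg counts will be calculated for the two treatment arms before and after treatment to assess the corresponding ERRs".

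The sample-size section (8.2) says which ERRs the team expects. It reports simulations with cure rates of 10% and 20%, and adds that this "translates roughly into ERRs of 38% and 64" percent.

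**The concern.** A geometric mean with an offset of 1 is exp[(1/n) Σ log(EPG + 1)] − 1, with the averaging inside the exponent. The printed term is (1/n) exp[Σ log(EPG + 1)] − 1. Because the exponential of a sum of logs is a product, the printed term multiplies together every child's (EPG + 1), divides by n and subtracts 1. It is neither of the means named in section 4.3.3.

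The ERR is the primary endpoint, and this is its only formula. Anyone who programs it literally, including someone reproducing the analysis from the public plan, cannot tell a 38% arm from a 64% arm. Every bootstrap replicate has the same fault, so the interval for the difference either shrinks to a point at 0 or is undefined.

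**Working it through.** **Inputs from the plan.** Expected ERRs are 38% and 64%, with 160 children per arm for 80% power and 200 recruited per arm (section 8.2). 200 less the 10% allowed for loss is 180. The minimum baseline count is 50 EPG in section 5.2 and 100 EPG in section 4.3.3. These two must be reconciled, but the finding holds under either.

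**Input not in the plan.** The baseline geometric mean is not given. I use 200 EPG for illustration and then a range of 100 to 1,000.

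**The plan's own figures.** The 160 per arm came from resampling patient data that are not in the documents, so it can be neither confirmed nor refuted here. The step to 200 is consistent: 160 × 1.10 × 1.14 = 200.6, or 160/0.9 = 178 and 178 × 1.14 = 203. For this point, what matters is whether the printed formula can return ERRs of 38% and 64% at these sizes.

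**Step 1: three children.** Take baseline counts of 100, 200 and 400 EPG and follow-up counts of 50, 100 and 200, so that every child's count halves.

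- Printed baseline term: (101 × 201 × 401)/3 − 1 = 2,713,566
- Printed follow-up term: (51 × 101 × 201)/3 − 1 = 345,116
- Printed ERR: 1 − 345,116/2,713,566 = 87.3%
- With 1/n in the exponent, the geometric means are 200.17 and 100.16, and the ERR is 50.0%

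**Step 2: general form.** Write GMb and GMf for the baseline and follow-up geometric means. The exponential of the summed logs equals (GM + 1)^n. In the ratio 1/n cancels and the −1 is negligible once the product is large, so

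printed ERR ≈ 1 − [(GMf + 1)/(GMb + 1)]^n.

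The exponent n should not be there.

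**Step 3: the planned ERRs.** With GMb = 200, a true ERR of 38% means GMf = 124 and a base of 125/201. A true ERR of 64% means GMf = 72 and a base of 73/201.

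| n per arm | printed ERR, true 38% | printed ERR, true 64% |
|---|---|---|
| 2 | 61% | 87% |
| 10 | 99.1% | 99.996% |
| 160 | 1 − about 10^−33 | 1 − about 10^−70 |
| 200 | 1 − about 10^−41 | 1 − about 10^−88 |

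At 160 or 200 per arm both values are 100% in double precision and the difference is 0. Over baseline geometric means of 100 to 1,000 EPG, the shortfall from 100% at n = 160 stays near 10^−33 for the 38% arm and between about 10^−70 and 10^−71 for the 64% arm. Even a true ERR of 5% is returned as more than 99.9% at n = 160.

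**Step 4: overflow.** The exponential fails in double precision once its argument exceeds 709.78. The baseline argument is n × ln(GMb + 1):

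- GMb = 200, n = 180: 180 × ln(201) = 954.6, which overflows
- every child at 50 EPG, n = 200: 200 × ln(51) = 786.4, which overflows (certain from n = 181); at n = 160 it is 629.1
- every child at 100 EPG, n = 160: 160 × ln(101) = 738.4, which overflows (certain from n = 154)

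With GMb = 200 and n = 180, the follow-up arguments are 180 × ln(125) = 869.1 and 180 × ln(73) = 772.3. Both terms overflow in both arms, and each ERR is infinity divided by infinity.

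I also simulated trials of 160 per arm under five assumed lognormal baseline distributions (baseline geometric mean about 194 to 327 EPG). In 98% to 100% of trials, at least one arm had a non-finite ERR when the formula was evaluated directly.

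**Step 5: after correction.** With 1/n in the exponent, the same simulated scenarios gave ERRs of 38–43% at a cure rate of 10% and 65–68% at 20%, close to the plan's 38% and 64%.

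**The case against.** The strongest reply is that this is a typesetting slip with an obvious reading. The sentence before the formula says geometric mean, and the +1 inside the log with the −1 outside makes sense only for a geometric mean with an offset. The ERRs of 38% and 64% cannot have come from the printed expression at the planned size, so the team's simulations presumably used a working version. Literal code would also give itself away at the first run, with 100% in both arms or a non-finite value. All of this stands, and it limits the finding to the written specification. It does not make the formula correct.

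The text was also extracted from a PDF by a program, and a stacked 1/n at the start of an exponent could have been placed at the wrong level. Identical placement in both terms makes a random misreading less likely but does not exclude a systematic one. The original page should be checked.

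Two limits on the size also stand. A result near 100% requires the geometric mean to fall in that arm, as the plan assumes; if it rose, the formula would give a huge negative value. Working on the log scale avoids overflow and, with equal n, keeps the sign of the difference between arms, but the ERR values remain meaningless.

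**Conclusion.** The formula is wrong as written. That it is not a geometric mean follows from algebra alone. That it cannot return the planned ERRs at 160 to 200 per arm holds for every baseline geometric mean examined from 100 to 1,000 EPG, provided egg counts fall in both arms. Overflow depends on n, on the baseline counts and on evaluating the exponential directly; it is certain at 200 per arm under either minimum count.

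The conclusion is conditional on the original page showing 1/n where the extracted text has it. It says nothing against the 160 per arm or the analysis code. Because this is the only formula for the primary endpoint and the superiority decision rests on it, it must be corrected.

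**What to change.** In section 8.3, confirm the placement on the original page and replace the formula with

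ERR = 1 − {exp[(1/n) Σ log(EPG at follow-up + 1)] − 1} / {exp[(1/n) Σ log(EPG at baseline + 1)] − 1},

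stating that both sums run over the same n children in the arm, namely those in the analysis set with follow-up counts. Check the analysis program against the three-child example: it should return 50.0%, not 87.3%.

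The cost is one formula. Section 9.1 requires the change to be documented in writing and, if handled as a protocol amendment, approved by the PI and submitted to the ethics committee. Design, data collection and sample size do not change.

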4.4. Measure to minimize bias

Study participants eligible for treatment will be randomly assigned to one of the two treatment arms using a computer-generated stratified block randomization code. The random allocation sequence with varying random blocks of four or eight and stratified by 2 levels of baseline infection intensity (light: 1-1999 EPG, and moderate plus heavy: ≥ 2000 EPG hookworm infections) will be provided by a statistician. Both treatment arms will have an equal number of participants with light infection intensity, although the number of light *versus* moderate/heavy infections are not expected to be equal within each arm, depending on the distribution of infection intensity in the recruited cohort.

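### The primary ERR comparison is valid, but it names no use of the randomisation strata and fixes the log-scale baseline slope at about 1, which may give up a little precision

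*Combined protocol and SAP*

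**What the plan says.** Section 8.3 defines the primary estimate by arm: "Geometric mean egg counts will be calculated for the different treatment arms before and after treatment to assess the corresponding ERRs". For the interval it says: "Bootstrap resampling with 5,000 replicates will be used to calculate 95% confidence intervals (CIs) for ERRs and the difference between the two ERRs". Neither sentence mentions strata, covariates or how children are resampled, and the synopsis adds nothing on this.

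Section 4.4 says that the allocation sequence is "stratified by 2 levels of baseline infection intensity", with the cut at 2000 EPG. In Section 8.3 the strata appear only for cure rate, a secondary endpoint: "In a subsequent analysis an adjusted logistic regression (adjustment for age, sex, weight and strata) will be performed".

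The data for an adjusted analysis will exist. Section 4.3.3 says: "EPG will be assessed by adding up the egg counts from the quadruplicate Kato-Katz thick smears and multiplying this number by a factor of six". Two baseline stool samples are an inclusion criterion (Section 5.2).

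**The concern.** There are two related issues.

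First, the plan restricts randomisation by baseline intensity but describes no matching feature in its only primary analysis. If whole arms are resampled, the mix of light and moderate/heavy infections varies between replicates, although the design held it nearly equal between arms. The interval then carries slightly more variation than the design produces.

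Second, the ERR is a ratio to the arm's own baseline. On the log scale that is a change score, in which a one-unit difference in log baseline is taken to carry over fully to follow-up. Section 8.2 plans for cure rates of 10% and 20%, and zero counts can move the slope either way. They flatten it if cure is unrelated to intensity, and steepen it to 1 or above if light infections clear more often. A regression that estimates the slope can then be somewhat more precise with the same children.

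What is at stake is a small amount of power on the primary comparison and its consistency with the design. The validity of the result is not at stake.

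**Working it through.** **Inputs from the documents.** Section 8.2 gives ERRs of 38% and 64%, cure rates of 10% and 20%, 80% power, 160 evaluable children per arm, 10% loss, a 14% margin and 200 recruited per arm. Section 8.3 gives a 95% interval, taken here as two-sided 5% with zero as the null for a difference. The printed ERR formula is read as the geometric mean that the text describes.

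**Inputs not in the documents.** The slope β of log follow-up EPG on log baseline EPG, the SD of log baseline EPG (SD_b) and the SD of the log change are not given. All three are assumed or back-solved below.

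**1. The plan's own figure.** The 160 comes from resampling an external data set and cannot be rebuilt from the documents. The inflation step can: 160 × 1.10 × 1.14 = 200.6, against 200.

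**2. SD of the log change implied by 160 per arm at 80% power.**
- Log-ratio scale: ln(0.62/0.36) = 0.544. Solving 160 = 2 × (1.960 + 0.842)² × SD² / 0.544² gives SD = 1.74.
- ERR-difference scale (delta method): the standard error needed is 0.26/2.802 = 0.0928. Solving 0.0928² = (0.62² + 0.36²) × SD² / 160 gives SD = 1.64.

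**3. Precision forgone.** With Y the log follow-up and B the log baseline, Var(Y − B) = residual variance + (β − 1)² × SD_b². Estimating the slope removes the last term, so the proportional reduction is (β − 1)² × SD_b² / SD². This is a large-sample result for the log scale and an approximation for the ERR difference. For SD_b from 0.7 to 1.3 and SD from 1.64 to 1.74:

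| Assumed slope | Variance reduction | Equivalent n per arm (from 160) | Power at 160 |
|---|---|---|---|
| 1.0 | 0% | 160 | 80.0% |
| 0.8 or 1.2 | 0.7-2.5% | 156-159 | 80-81% |
| 0.7 | 1.5-5.7% | 151-158 | 81-82% |
| 0.5 | 4-16% | 135-154 | 82-86% |

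For example, with β = 0.5, SD_b = 1.3 and SD = 1.64: 0.25 × 1.69 / 2.69 = 0.157, and 160 × (1 − 0.157) = 135.

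**4. Simulated egg counts at the planning values.** Twenty-two assumed scenarios were calibrated to about 10%/20% cure and 38%/64% ERR at 160 per arm. They used a true log-mean EPG of 5.3-5.8, SD 1.2, day-to-day gamma variation (shape 1.5) and an entry threshold of 50 or 100 EPG, because the documents state both. Arm slopes ran from 0.64 to 1.30. The adjusted analysis matched the unadjusted variance with 156.6-160.0 per arm, a reduction of 0-2.1% (1 − 156.6/160 = 2.1%). Power rose by at most 0.8 points. Adjusting for the two strata alone gave 158.9-160.0 per arm, at most 0.7%. Three of the scenarios show the pattern (log-mean 5.8, threshold 50):

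| Link between light infection and cure | Arm slopes | Equivalent n | Power, unadjusted to adjusted |
|---|---|---|---|
| None | 0.74, 0.64 | 156.6 | 0.520 to 0.528 |
| Intermediate | 0.92, 1.01 | 159.8 | 0.606 to 0.607 |
| Strong | 1.05, 1.23 | 159.2 | 0.611 to 0.613 |

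Absolute power in this set (45-68%) reflects the assumed distributions and is not evidence against the plan's 80%.

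**5. Further assumed scenarios.**
- Sixteen at 180 per arm (200 × 0.9) gave adjusted/unadjusted variance ratios of 0.963-1.006, with the mean ERR difference unchanged to within 0.002.
- Seven others at 180 per arm (6,000 trials each) gave 0.941, 0.980, 0.933, 0.881, 1.003, 0.987 and 0.972.
- Thirty-six larger-sample scenarios gave 0.925-1.000.

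The separate effect of stratifying the bootstrap was not simulated.

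**The case against.** The strongest defence is that nothing here is wrong. ERR is the declared endpoint, baseline EPG is its denominator, and stratified randomisation already limits chance imbalance in intensity. The sample size carries a 14% margin beyond loss to follow-up. A model-based ERR is a legitimate alternative, not a requirement. All of this stands, and it limits the point to a small efficiency and consistency gain.

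Three stronger readings are tempting, and the documents support none of them.
- **The plan discards the baseline or is invalid.** It does neither. It uses the baseline with a fixed slope, and an unstratified bootstrap errs towards a slightly wide interval.
- **The bootstrap ignores the strata.** Section 8.3 does not describe the resampling scheme. What can be said is that the scheme is unspecified.
- **About 12% of variance is lost.** One favourable scenario gave a ratio of 0.881, which is worth about 180 × 0.119 = 21 children per arm, and a power example from that set rose from 0.858 to 0.895. Nothing in the documents makes that scenario the expected one, and the set calibrated to the planning values stayed at 2.1% or less.

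Nor is the adjusted interval always at least as narrow. The large-sample guarantee belongs to the difference in mean logs under equal allocation. For the ERR difference, ratios of 1.003 and 1.006 occurred. These are trivial, but they rule out an unconditional promise.

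**Conclusion.** The point holds as a minor one. The primary comparison is valid, names no use of the strata that restricted randomisation, and fixes the log-scale slope at about 1. If the true slope differs from 1, it may forgo about 0-4% of variance in most of the assumed scenarios. The loss is essentially nil when the slope is near 1. It is larger, up to about 16% in the algebra, only with a shallow slope and wide baseline spread. The strata alone contribute very little.

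A reader might infer that the trial is materially underpowered by this choice. The documents do not support that: they give no slope, SD or baseline/follow-up correlation, and the assumed slopes fall on both sides of 1. The case for acting rests on low cost and consistency with the design, since the effect measure stays the same.

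**What to change.** In Section 8.3:
- State that bootstrap samples are drawn within treatment arm and randomisation stratum.
- Prespecify, before the outcome data are seen, a regression of log(follow-up EPG + 1) on treatment, log(baseline EPG + 1) and stratum. Standardise the arm means to the pooled baseline, convert them to ERRs and their difference, and refit the model in each of the 5,000 replicates.
- Report the unadjusted ERRs and their difference alongside.

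Timing decides the status of the adjusted result. This version is dated 26.08.2019, whereas the synopsis planned the last participant out in 05/2019, and the documents do not say whether outcome data had been seen. If the primary analysis can no longer be changed, the adjusted ERR difference should be the supporting analysis.

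The cost is slightly more analysis code and possibly ethics committee approval of an amendment (Section 9.1). No new data are needed, and a finite sample may show no gain.

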The overall goal of this study is to determine if a chewable formulation of mebendazole is superior to a swallowable formulation tablet of mebendazole (standard of care) against hookworm in children.

We hypothesize that the chewable formulation of mebendazole has a higher efficacy against hookworm infections than the swallowable one. Better absorption and bioavailability as well as better palatability are expected to contribute to superior efficacy.

The **primary objective** of the study is to compare the egg reduction rates (ERRs) of two different mebendazole formulations against hookworm in children (3 - 12 years old): (i) 500 mg of a single chewable mebendazole tablet and (ii) 500 mg of a single solid mebendazole tablet.

The **secondary objectives** of the trial are:

- To evaluate the safety and tolerability of the two formulations
- To evaluate the CR of the two formulations against hookworm
- To determine the CRs and ERRs against *Ascaris lumbricoides* and *Trichuris trichiura*
- To investigate the acceptability and age-appropriateness of both formulation when administered to children between 3 and 12 years of age

The **exploratory objectives** of this study are:

- To assess how well caregivers understand the clinical trials aim, procedures, their rights, risks and potential benefits

- To compare the effect of different methods of providing information on their understanding of the clinical trial

4. Methodology

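### The primary superiority rule compares a difference in egg reduction rates with 1 instead of 0 and states no direction, so as written it is met almost whatever the data show

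*Combined protocol and SAP*

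**What the plan says.** Section 3 sets the aim: to "determine if a chewable formulation of mebendazole is superior to a swallowable formulation tablet of mebendazole". It adds the hypothesis that the chewable tablet is the more effective one.

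Section 8.2 treats the primary outcome as a difference between the two ERRs. It plans on ERRs of about 38% and 64%, and concludes: "We estimated that 160 patients per arm are required to detect a statistical significant difference with 80% power".

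Section 8.3 defines the ERR as 1 minus the ratio of the follow-up to the baseline geometric mean, which is a fraction with a maximum of 1. For inference it says: "Bootstrap resampling with 5,000 replicates will be used to calculate 95% confidence intervals (CIs) for ERRs and the difference between the two ERRs". The decision rule follows directly: "Superiority will be claimed if the 95% confidence interval of the difference in ERRs does not include unity (primary hypothesis".

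The synopsis repeats the bootstrap method but gives no decision rule. No section states a null value of 0, and none redefines the effect measure as a ratio of ERRs. Cure rates and adverse events have no claim rule, so this sentence is the trial's only confirmatory criterion.

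**The concern.** There are two separate defects in the sentence.

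- **Null value.** Two equally effective tablets give a difference of 0, so a superiority test has to ask whether the CI excludes 0. Asking whether it excludes 1 tests a value that the difference can hardly reach.
- **Direction.** The sentence gives neither the order of subtraction nor the side on which the CI must lie. A CI lying wholly below 0, with chewable worse, also excludes 1 and literally meets the criterion.

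If the rule were applied as worded, the superiority claim would not separate a better tablet from an equal or a worse one. If it were silently reinterpreted at analysis, the primary criterion would in effect be chosen after the data were available, which prespecification is meant to prevent.

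**Working it through.** **Inputs from the plan.** ERR on the fraction scale, 95% bootstrap CI for the difference, superiority if 1 is excluded (8.3); planning ERRs 0.38 and 0.64, cure rates 10% and 20%, 160 evaluable and 200 recruited per arm (8.2); chewable expected to be better (section 3).

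**The plan's own figure.** The 160 per arm came from resampling egg counts of an earlier trial. Those counts are not in the documents, so the figure cannot be reproduced. The inflation can: 160 × 1.10 × 1.14 = 200.6, about 200. Nothing below depends on the 160 being right or wrong.

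**Bound on the difference.** Let r = GM(follow-up)/GM(baseline) be the residual egg ratio, so ERR = 1 − r. Then

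D = ERR(chewable) − ERR(swallowable) = r(swallowable) − r(chewable).

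- Planned: 0.62 − 0.36 = 0.26.
- Ceiling, with a perfect chewable tablet: 0.62 − 0 = 0.62.
- D = 1 would need, for example, ERR 100% against 0%.

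The value 1 lies beyond what the trial can show at its own planning values. The CI excludes 1 because it lies wholly below it, not because chewable performed well.

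**Simulation.** The documents give no egg-count distributions, so these are assumptions: log-normal baseline EPG around 350 with a floor of 50; log-SD 1.0–1.2 at baseline and 1.0–1.6 for the change; follow-up calibrated to the plan's pairs of cure rate and ERR; the usual geometric mean with 1/n inside the exponent. (The placement of 1/n in the printed formula is a separate matter.) There were three SD settings, 160 and 200 per arm, 500 trials per configuration, and percentile CIs from 1,000 resamples. Ranges are over configurations.

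| True ERR, swallowable / chewable | As written: CI excludes 1 | CI excludes 0, no direction | Lower limit of D above 0 | Percent scale: CI excludes 1 point |
|---|---|---|---|---|
| Equal (38/38, 64/64) | 100% | 4.4–6.8% | 2.2–4.0% | 4.8–7.0% |
| Chewable worse (64/38) | 100% | 48.2–61.4% | 0–0.2% | 50.4–65.4% |
| Planned effect (38/64) | 98.6–100% | 47.0–64.2% | 47.0–64.2% | 44.6–61.2% |

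- Equal ERRs: 2 scenarios × 3 SD settings × 2 sizes × 500 = 6,000 trials. All met the written rule; the highest upper limit was 0.986.
- Chewable worse: 3 × 2 × 500 = 3,000 trials. All met the written rule; the highest upper limit was 0.612.
- No lower limit exceeded 1 in any scenario. The written rule failed only at the planned effect with 160 per arm, in 0.6% and 1.4% of trials under the two larger SD settings, because an upper limit passed 1. So the only trials denied the claim were ones in which chewable was truly better.
- Typical CIs at 160 per arm (SDs 1.0/1.0): −0.28 to 0.28 with equal ERRs of 38%, and 0.02 to 0.52 at the planned effect.

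A separate run with 180 analysed per arm (200 less 10%) gave the same picture: 1 was excluded in 150 of 150 no-effect trials and 150 of 150 planned-effect trials.

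**The case against.** The best defence is that the intention is clear. The rule speaks of superiority and of the primary hypothesis, and section 3 defines that as chewable being better. Section 8.2 claims 80% power at 160 per arm, which would be meaningless under a rule that is met nearly every time. On this view, unity is a word carried over from ratio measures and no statistician would apply it literally. That is probably true, and it makes the intended rule recoverable. It does not put the null value of 0, the order of subtraction or the relevant limit into the operative sentence.

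A second point is scale. Section 8.2 quotes ERRs in percent, and in percentage points the rule would test against 1 point. The figure of about 100% with equal ERRs then falls to about 5–7%. This stands: the 100% applies to the fraction scale, which is the scale of the formula in 8.3. The percent reading does not rescue the rule. A margin of 1 point appears nowhere else in the plan, and the rule would still be met in 50–65% of trials with chewable worse.

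Third, the simulations rest on assumed variances, and 150 of 150 alone leaves an upper bound of about 3/150 = 2% on the rate at which the rule is not met. That is fair, but the algebraic bound carries the argument, and the results for equal ERRs and for chewable worse did not move over the SD range.

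Lastly, readers would still see each arm's ERR and the CI for the difference. So the reported estimates remain informative; it is the superiority claim that does not.

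**Conclusion.** The concern holds. The only confirmatory criterion uses the wrong null value and carries no direction. Taken literally on the fraction scale of 8.3, it gives a false-positive rate of about 100% instead of a nominal 2.5% in favour of chewable, and it would also label a worse chewable tablet superior. That result follows from the bound on the difference and does not depend on the exact egg-count distribution within the range tried.

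Both parts need correcting. Replacing 1 by 0 restores roughly 5% error in total with equal ERRs, but still allows a claim in about half or more of the trials with chewable worse. With the null at 0 and the direction stated, the rates are about 2–4% with equal ERRs and at most 0.2% with chewable worse.

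The 47–64% shown for the corrected rule at the planned effect depends on the assumed SDs and is not evidence against the sample size. Although probably a slip, the wording must be corrected because the primary claim rests on it.

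**What to change.** Replace the decision sentence in 8.3 with, for example:

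*Let D = ERR(chewable) − ERR(swallowable), with both ERRs expressed as fractions. The chewable tablet is declared superior only if the lower limit of the two-sided 95% bootstrap CI for D is greater than 0.*

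Repeating the rule in the synopsis, which now has none, would keep the two places aligned.

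The cost is one sentence. Data collection and the bootstrap are unaffected. The recruitment target need not change if the simulations behind 8.2 already tested against 0; because 8.2 states neither the test nor its sidedness, the trial statistician should confirm this. Section 9.1 requires a written amendment, signed by the PI and sent to the ethics committee. This version is dated 26.08.2019, after the 05/2019 planned for the last participant out, so the record should also state whether the correction was made before any comparative results were seen.
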